12.8. Planned interim analysis and data monitoring

There are no interim analyses planned for this small, short-term study. In addition to standard monitoring by the sponsor during the trial, there will be a blind data review by the trial statistician prior to the final database lock.

12.9. Determination of sample size and randomization method

We will allocate the patients to arm A if the patient's naive CD4⁺ T-cell frequency is normal for their age and gender. In our previous pilot study 42% of comparable RA patients had abnormal frequency values, of whom 25% responded to MTX at 6 months compared to 68% of those with normal values. Those with abnormal values will be (randomly permuted block) randomised 1:1 to arm B or C, therefore this would result in an approximate 2.75:1 ratio of patients in arms A and B. For the primary outcome of clinical remission at 24 weeks, at the 5% level of significance, to achieve 80% power to detect a difference between the target proportions of patients achieving clinical remission in arms A (68%) and B (25%)[25], a total of 53 patients would be required, assuming binary logistic regression with a variance inflation factor of 1.05 estimated from pilot data. We will increase the sample size to n=60 to account for 10% drop-out. The total number needed to be recruited to the study would therefore be 76 (44 in arm A, 16 in arm B and 16 in arm C).

To have a more robust estimate of the proportion of clinical remission in arm B and C, recruitment will continue until at least 34 and no more than 60 patients with abnormal T-cell values have been randomised 1:1 to arm B or C, and there are at least 46 patients in arm A. Thus the total sample size for the study is anticipated to be between 76 (approximately A=44, B=16, C=16) and 106 patients (approximately A=46, B=30, C=30). In the case where recruitment within Arm A is disproportionately recruiting more than Arm B or C, recruitment will stop within Arm A once minimum recruitment number has been reached. Patients will not be disadvantaged as they will still receive Treat to Target care.

12.10. Procedure for un-blinding the study prior to analysis

The trial statistician will remain blind to naive CD4⁺ T-cell status (normal/abnormal) and treatment arm during an initial review of the data prior to the final database lock. Once the review is complete, any necessary amendments to correct data entry errors have been made, and the SAP updated to reflect any additional sensitivity analyses required, the date the statistician received the identification codes for the 3 study arms will be formally recorded in the trial documentation before the analysis can begin.

13. ETHICS AND REGULATORY REQUIREMENTS

13.1. Good Clinical Practice

This study will be conducted in accordance with applicable laws and regulations including, but not limited to, the International Conference on Harmonisation (ICH) Guideline for Good Clinical Practice (GCP) and the recommendations guiding ethical research involving human subjects adopted by the 18th World Medical Assembly, Helsinki, Finland, 1964, amended at the 48th General Assembly, Somerset West Republic of South Africa, October 1996. The Research Ethics Committee (REC) and MHRA must review and approve the protocol and informed consent form before any subjects are enrolled. Before any protocol-required procedures are performed, the subject must sign and date the REC-approved informed consent form. The right of a patient to refuse participation without giving reasons must be respected. The patient must remain free to withdraw at any time from the study without giving reasons and without prejudicing his/her further treatment. The study will be submitted to and approved by a main Research Ethics Committee (REC) and the appropriate regulatory authorities prior to entering patients into the study.

13.2. Delegation of Investigator duties

The Principal Investigator should ensure that all persons assisting with the trial are adequately qualified and informed about the protocol, any amendments to the protocol, the study treatments, and their trial related duties and functions.

The Principal Investigator should maintain a delegation log of co-investigators and other appropriately qualified persons to whom he or she has delegated significant trial-related duties. The delegation log will be kept within the investigator site file.

13.3. Subject information and informed consent

Before being enrolled in the clinical study, subjects must consent to participate after the nature, scope, and possible consequences of the clinical study have been explained in a form understandable to them.

An informed consent document (Patient Information Leaflet) that includes both information about the study and the consent form will be prepared and given to the subject at least 24 hours prior to the screening visit. This document will contain all the elements required by the ICH E6 Guideline for Good Clinical Practice and any additional elements required by local regulations. The document must be translated (by an independent interpreter) into a language understandable to the subject and must specify who informed the subject. Where required by local law, the person who informs the subject must be a physician.

At the screening visit, patients will be given the opportunity to ask questions and the nature and objectives of the study will be explained. A research nurse may help in this process but the study doctor is responsible for the informed consent discussions.

After reading the informed consent document, the subject must give consent in writing. The subject's consent must be confirmed at the time of consent by the personally dated signature of the subject and by the personally dated signature of the person conducting the informed consent discussions, the study doctor.

The original signed consent document will be retained in the Study Files. Other copies of the consent form are required:

- One copy of the informed consent document will be kept in the patient's clinical notes.
- One copy will be given to the patient.

Consent is an ongoing process and will be reassessed at each study visit.

The Investigator will not undertake any measures specifically required only for the clinical study until valid consent has been obtained.

The Investigator must inform the subject's primary physician about the subject's participation in the trial if the subject has a primary physician and if the subject agrees to the primary physician being informed.

13.4. Subject confidentiality

Only the subject number will be recorded in the case report form, and if the subject name appears on any other document (e.g. laboratory report), it must be obliterated on the copy of the document to be supplied to anyone outside the clinical care team. The subjects will be informed that representatives of the Sponsor, Research Ethics Committee (REC) or regulatory authorities may inspect their medical records to verify the information collected, and that all personal information made available for inspection will be handled in strictest confidence.

All information collected during the course of the trial will be kept strictly confidential.

Information will be held securely on paper and also electronically.

The Leeds Institute for Rheumatology and Musculoskeletal Medicine/Leeds Musculoskeletal Biomedical Research Unit will comply with all aspects of the Data Protection Act 2018.

The Principle Investigator at each site will maintain a personal subject identification list (subject numbers with the corresponding subject names) to enable records to be identified.

13.5. Approval of clinical study protocol and amendments

Before the start of the study, the clinical study protocol, informed consent document, and any other appropriate documents will be submitted to the REC, the MHRA and the Sponsor with a cover letter or a form listing the documents submitted, their dates of issue, and the site (or region or area of jurisdiction, as applicable) for which approval is sought. If applicable, the documents will also be submitted to the authorities, in accordance with local legal requirements.

Investigational products can only be supplied Sponsor after documentation on all ethical and legal requirements for starting the study has been received by the product provider.

Before the first subject is enrolled in the study, all ethical and legal requirements must be met, including approval of the study by the NHS organisation via the Sponsor Research and Development department, the REC, the MHRA and HRA.

Amendments must be evaluated to determine whether formal approval must be sought and whether the informed consent document should be revised, thus all protocol amendments and administrative changes must first be discussed with and approved by the Sponsor before being submitted to the REC and the MHRA, in accordance with legal requirements.

The Investigator must keep a record of all communication with the REC, the MHRA, and the Sponsor. This also applies to any communication between the Investigator (or the coordinating Investigator, if applicable) and the authorities.

13.6. Protocol amendments

Requests for any amendments to the study must be sent to the Sponsor and R&I QA office by the Chief Investigator or a delegated individual. The Sponsor will determine whether said amendments are substantial or non-substantial prior to their submission to the appropriate bodies for approval. Patients should be re-consented to the study if the amendments affect the information they have received, patient safety, or if the change alters the type or quality of the data collected for the study. Patients should only be re-consented AFTER an amendment has been fully approved.

13.7. Ongoing information for MHRA/REC

In accordance with CTIMP regulations and Sponsor policy, the Investigator (or their delegate) must submit to the MHRA, REC and the Sponsor:

- Information on suspected unexpected serious adverse reactions (SUSARs) from the Investigator's site, as soon as possible and always within 24 hours of the research team becoming aware of them.
- Expedited safety reports, as soon as possible and always within the necessary reporting deadline.
- Development Safety Update Reports (DSUR) to both REC and MHRA (also referred to as Annual Safety Reports).
- Annual reports on the progress of the study to the REC.
- The Declaration of the End of Trial Notification form.

14. FINANCE AND INSURANCE

14.1. Indemnity and insurance

The University of Leeds is able to provide insurance to cover for liabilities and prospective liabilities arising from negligent harm. In certain circumstances, we provide insurance cover for claims arising from non-negligent harm.

Clinical negligence indemnification will rest with The Leeds Teaching Hospitals NHS Trust under standard NHS arrangements.

Further details of liability and insurance provisions for this study are given in separate agreements.

14.2. Financial disclosure

None of the investigators or members of the research team have any financial involvement with the sponsorship or funding bodies or will receive personal benefits, incentives or payment over and above normal salary.

15. PUBLICATION

The trial will be registered with an authorised registry, according to ICMJE Guidelines, prior to the start of recruitment.

The success of the trial depends upon the collaboration of all patients. For this reason, credit for the main results will be given to all those who have collaborated in the trial, through authorship and contributor ship. Uniform requirements for authorship for manuscripts submitted to medical journals will guide authorship decisions. These state that authorship credit should be based only on substantial contribution to: Conception and design, or acquisition of data, or analysis and interpretation of data, ^[1]page drafting the article or revising it critically for important intellectual content, and final approval of the version to be published, and ^[2]that all these conditions must be met (www.icmje.org).

In light of this, the Chief Investigator, and relevant staff will be named as authors in any publication. In addition, all collaborators will be listed as contributors for the main trial publication, giving details of roles in planning, conducting and reporting the trial.

To maintain the scientific integrity of the trial, data will not be released prior to the end of the trial, either for trial publication or oral presentation purposes, without the permission of the Trial Steering Committee or the Chief Investigator. In addition, individual collaborators must not publish data directly relevant to the questions posed in the trial until the main results of the trial have been published and following written consent from the Sponsor.

24. Aletaha, D., et al., *2010 Rheumatoid arthritis classification criteria: an American College of Rheumatology/European League Against Rheumatism collaborative initiative*. Arthritis Rheum, 2010. **62**(9): p. 2569-81.
25. Smolen, J.S., et al., *A simplified disease activity index for rheumatoid arthritis for use in clinical practice*. Rheumatology (Oxford), 2003. **42**(2): p. 244-57.

Appendix 1

Scale for interpreting T-cell results based on age

"Patients' naïve T-cell frequency (%) will be compared to the level expected for their age according to the following formula derived from 106 healthy controls: $(-0.54 * \text{age}) + 63.19$.

A patient whose naïve T-cell level is at or above this value will be considered to have a normal T-cell result; a patient with levels below the age-expected value will be considered to have an abnormal result."

Age	Normality Threshold	Age	Normality Threshold
18	53.47	60	30.79
19	52.93	61	30.25
20	52.39	62	29.71
21	51.85	63	29.17
22	51.31	64	28.63
23	50.77	65	28.09
24	50.23	66	27.55
25	49.69	67	27.01
26	49.15	68	26.47
28	48.07	69	25.93
29	47.53	70	25.39
30	46.99	71	24.85
31	46.45	72	24.31
32	45.91	73	23.77
33	45.37	74	23.23
34	44.83	75	22.69
35	44.29	76	22.15
36	43.75	77	21.61
37	43.21	78	21.07
38	42.67	79	20.53
39	42.13	80	19.99
40	41.59	81	19.45
41	41.05	82	18.91
42	40.51	83	18.37
43	39.97	84	17.83
44	39.43	85	17.29
45	38.89	86	16.75
46	38.35	87	16.21
47	37.81	88	15.67
48	37.27	89	15.13
49	36.73	90	14.59
50	36.19	91	14.05
51	35.65	92	13.51
52	35.11	93	12.97
53	34.57	94	12.43
54	34.03	95	11.89
55	33.49	96	11.35
56	32.95	97	10.81
57	32.41	98	10.27
58	31.87	99	9.73
59	31.33

## 1. Document scope and relevant SOPs and guidance documents

This statistical analysis plan (SAP) was drafted prior to the completion of database lock and was prepared according to YTU SOPs and guidance documents.

## 2. Definition of terms/acronyms

Term	Definition
ACPA	Anti-citrullinated protein antibody
AE	Adverse event
CDAI	Clinical Disease Activity Index
CI	Confidence interval
CRF	Case Report Form
CRP	C-Reactive Protein
DMARD	Disease modifying anti-rheumatic drug
EMS	Early Morning Stiffness
ESR	Erythrocyte Sedimentation Rate
HAQ	Health Assessment Questionnaire
ICH	International Conference On Harmonisation
IMP	Investigational Medicinal Product
LFT	Liver function tests
LIRMM	Leeds Institute of Rheumatic and Musculoskeletal Medicine
MTX	Methotrexate
RA	Rheumatoid Arthritis
SAE	Serious Adverse Event
SD	Standard Deviation
SDAI	Simplified Disease Activity Index
SJC	Swollen Joint Count
T2T	Treat to target
TJC	Tender Joint Count
VAS	Visual Analogue Scale

### **3. Background and Rationale**

The current optimal therapeutic approach in early Rheumatoid Arthritis (RA) is to start Methotrexate (MTX) to target inflammation and induce remission. Prediction of MTX therapy response remains a key clinical need to enable the identification of patients who would benefit from an alternative, more aggressive treatment strategy. Multiple predictors of remission with MTX have been reported over the years but none have entered routine clinical practice.

It has previously been reported by this study team that T-cell phenotyping at baseline could predict remission in disease modifying anti-rheumatic drug (DMARD)-naïve early RA treated with MTX. Reduced naïve CD4+ T cell frequency was the most predictive factor, using both a pilot and a replication cohort. The data confirmed the potential value of using naïve CD4+ T-cells as a biomarker of MTX induced remission in early RA. The clinical utility of measuring T-cell subsets is therefore strongly indicated by these data and suggests that measurement of T-cell subsets can be used to rationalise the use of MTX as first-line therapy.

Predicting response to MTX has important clinical value to identify patients who will do well on MTX, but furthermore for directing those who will have a sub-optimal response to MTX to receive alternative therapy without any harmful delay and in line with the treat to target (T2T) principle.

This study aims to validate the clinical value of T-cell subset quantification for the prediction of MTX response in early RA, by stratified interventions based on baseline naïve CD4+ T-cell status.

This study aims to assess the clinical utility of T-cell stratification for rationalising treatment with MTX, therefore enabling early targeted treatment for those with a poorer prognosis based on their immunological status.

## 4. Design

This study is a single centre, phase IV, open-label, prospective, three-armed longitudinal cohort study with an embedded pilot randomised controlled trial that aims to assess whether MTX can be rationalised as a first-line treatment for DMARD-naïve early RA patients, according to baseline naïve CD4+ T-cell stratification. The three treatment arms are given in Table 1.

*Table 1: Trial arm descriptions*

Arm	Description
Arm A	Methotrexate as per standard practice for patients with a normal T-Cell frequency
Arm B	Methotrexate as per standard practice for patients with abnormal T-cell frequencies
Arm C	Methotrexate in combination with subcutaneous Etanercept in patients with abnormal T-cell frequencies

The flow of participants through the study can be seen in Figure 1. Full details of the background and trial design are presented in the protocol (version 6.0).

[figure not shown]

Figure 1: Schematic diagram showing study timeline and interventions

## 5. Trial Objectives

This study aims to assess the clinical utility of T-cell stratification for rationalising treatment with MTX, therefore enabling early targeted treatment for those with a poorer prognosis based on their immunological status. The study further aims to confirm and validate the clinical value of T-cell subset quantification for the prediction of MTX response in early RA, by stratified interventions based on baseline naïve CD4+ T- cell status.

The primary research hypothesis to be tested is whether a greater proportion of patients with normal naïve CD4+ T-cell frequencies for their age (Arm A) will achieve clinical remission after 24 weeks of first-line therapy with MTX and T2T care compared to those with abnormally low naïve CD4+ T-cell frequencies (Arm B).

## 5.1 Primary objective

To determine whether the proportion of patients achieving clinical remission after first-line treatment with MTX and T2T care differs according to naïve CD4+ T-cell frequency (normal/abnormal) at baseline (Arm A vs. Arm B).

## 5.2 Secondary objectives

- To determine the proportion of patients that achieve clinical remission for patients with abnormal baseline naïve CD4+ T-cell frequencies receiving etanercept + MTX (Arm C) to obtain preliminary proof-of-concept of superior response compared to MTX with T2T care (Arm B).
- To determine whether the proportion of patients that achieve imaging remission after first-line treatment with MTX differs according to naïve CD4+ T-cell frequency (normal/abnormal) at baseline (Arm A vs. Arm B).
- To determine the values of patient-reported outcomes (EMS, VAS scales, HAQ-DI) for patients with abnormal baseline naïve CD4+ T-cell frequencies receiving etanercept + MTX (Arm C) to obtain preliminary proof-of-concept of superior response compared to MTX with T2T care (Arm B).
- To determine whether patient-reported outcomes (EMS, VAS scales, HAQ-DI) after first-line treatment with MTX differ according to naïve CD4+ T-cell frequency (normal/abnormal) at baseline (Arm A vs. Arm B).
- To determine the proportion of patients that achieve imaging remission for patients with abnormal baseline naïve CD4+ T-cell frequencies receiving etanercept + MTX (Arm C) to obtain preliminary proof-of-concept of superior response compared to MTX with T2T care (Arm B).
- To determine the proportion of patients who normalize their T-cell status for patients with abnormal baseline naïve CD4+ T-cells receiving MTX with T2T care or etanercept + MTX (Arm B & Arm C).
- To determine whether the proportion of patients achieving sustained clinical remission differs between study arms.
- To determine whether the cumulative amount of corticosteroid use differs between study arms.

## 6. Follow-up

An overview of data collection, and the corresponding time frames, is detailed below and summarised in Table 9.1 in the protocol. Data will be collected by clinical research networks at study recruitment sites and directly from participants. Laboratory samples will be tested by the NHS laboratory in the Leeds Teaching Hospital Trust and the results then entered onto the electronic database by a member of the research team. Electronic data records such as x-ray and ultrasound records will be saved and stored in an appropriately secure location as described in the Source Data Verification form.

The total duration of the study for patients completing all visits from screening to final assessment will be 28 weeks maximum (up to 4 weeks between screening and baseline visit).

### 6.1 Week -4 to 0: Screening/Consent Data

- Eligibility
- Consent
- Demographics
- Clinical observations
- Medical history
- Laboratory tests
- Joint counts

- CDAI
- SDAI
- DAS28
- HAQ-DI
- VAS
- X-rays

## 6.2 Week 0: Baseline/IMP Commencement

- Medication, allergy, co-morbidity check
- Joint counts
- CDAI
- SDAI
- DAS28
- HAQ-DI
- VAS
- Laboratory tests
- Ultrasound
- AE recording
- DMARD as T2T
- Etanercept for Arm C

## 6.3 Week 4: Safety Visit

- Compliance with treatment
- Joint counts
- CDAI
- SDAI
- DAS28
- HAQ-DI
- VAS
- Laboratory tests
- AE recording
- DMARD management

## 6.4 Week 12: Secondary Outcomes

- Compliance with treatment
- Joint counts
- CDAI
- SDAI
- DAS28
- HAQ-DI
- VAS
- Laboratory tests
- AE recording
- DMARD management

## 6.5 Week 24: Primary Outcome Timepoint

- Compliance with treatment
- Joint counts
- CDAI
- SDAI

- DAS28
- HAQ-DI
- VAS
- Laboratory tests
- AE recording
- DMARD management
- Ultrasound

## 6.6 Withdrawal Visit

- Change of status

## 6.7 Unscheduled Visit

- AE recording
- Changes to treatment to be documented
- Compliance with treatment
- Clinical observations
- Medication, allergy and co-morbidity check
- Clinical assessment data
- Joint counts
- DAS28
- CDAI
- SDAI
- Laboratory tests
- Patient reported outcomes
- VAS
- HAQ-DI
- Ultrasound
- DMARD Management

# 7. Outcomes

## 7.1 Primary outcome

The primary outcome is the difference in the proportions of patients in clinical remission at 24 weeks of first-line methotrexate with T2T care between those with normal (Arm A) vs. abnormal (Arm B) naïve CD4+ T-cell frequencies at baseline.

The Disease Activity Score (DAS28ESR) is a combined index that measures disease activity in patients with Rheumatoid Arthritis (RA). It has been extensively validated for its use in clinical trials. It incorporates the tender 28-joint count (TJC28), the swollen 28-joint count (SJC28), erythrocyte sedimentation rate (ESR; mm/hour) and patient global/general health assessment VAS (mm).

The TJC28 and SJC28 are calculated from the assessment of the same 28 joints where each joint is determined to be either tender or not tender and either swollen or not swollen. The assessment will be performed by an independent assessor to minimize bias. Where possible, the same assessor should preferably perform the TJC and SJC for a given patient particularly during the study to minimize inter-observer variation.

Missing joint assessments will typically result in a missing count, however there are several cases of this (see CTT20 'multiple IJA missed entry') where they will be imputed as 0 due to confidence

expressed by the PI that the missing CRF fields should have indicated that the joint was not affected. In most of these cases only a few assessments were missing per participant.

The formula for DAS28(ESR) is:

$$DAS28(ESR) = 0.56\sqrt{TJC28} + 0.28\sqrt{SJC28} + 0.014(GH) + 0.70\ln(ESR)$$

The DAS28ESR will automatically be calculated within the MACRO system and computed at the analysis stage from the stored DAS28ESR components. Note that ESR values of 0 will be input as 0.001 to allow for them to be compatible with the DAS28 formula (i.e.  $\ln(0)$  is undefined). The DAS28ESR ranges from 0-10 with higher scores indicating greater disease activity. If any of the components are missing, then DAS28ESR will be missing. Clinical remission (primary endpoint) will be deemed to have been achieved if  $DAS28ESR \leq 2.6$ .

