4.2. Efficacy variables

- Tender joint count (range 0-28)
- Swollen joint count (range 0-28)
- Erythrocyte sedimentation rate (mm/hr)
- C-reactive protein (mg/L)
- DAS28 disease activity (derived; range 0-10)
- CDAI disease activity (derived; range 0-76)
- SDAI disease activity (derived; range 0-86)
- ACR/Boolean remission status (derived; yes/no)
- Physician global assessment VAS (mm; range 0-100)
- Early morning stiffness (EMS) (mins; range 0-720)
- Patient general health VAS (mm; range 0-100)
- Patient assessment of disease activity VAS (mm; range 0-100)
- Patient assessment of pain VAS (mm; range 0-100)

- Health Assessment Questionnaire Disability Index (HAQ-DI) (range 0-3)
- Number of joints scoring PD>0 (range 0-13 bilaterally), and tendons (range 0-5 bilaterally)
- Number of joints scoring GS>1 (range 0-13 bilaterally), and tendons (range 0-5 bilaterally)
- Naïve T-cell frequency (%)

4.3. *Exploratory biomarkers*

Serum and plasma samples collected at baseline and at Week 24 will also be stored (for future evaluation of disease categorization, auto-antibodies, inflammatory, immunological and vascular biomarkers and products of synovial, cartilage and bone turnover in this and future studies (subject to ethical review of such studies)).

A maximum of 40ml of blood will be drawn at each relevant visit. This will be collected, processed and stored in accordance with local practice.

4.4. *Safety variables*

- Number of patients experiencing SAEs and AEs. [L]
[SEP]
- Any clinically significant worsening of a pre-existing condition. [L]
[SEP]
- An AE occurring from overdose of an IMP, whether accidental or intentional. [L]
[SEP]
- An AE occurring from abuse (e.g. use for non-clinical reasons) of an IMP
- An AE that has been associated with the discontinuation of the use of an IMP

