8. METHODS OF ASSESSMENT

8.1. Assessment of primary efficacy variable:

Disease Activity Score (DAS28) Erythrocyte Sedimentation Rate method

- The Disease Activity Score (DAS28) is a combined index that measures disease activity in patients with Rheumatoid Arthritis (RA). It has been extensively validated for its use in clinical trials. It incorporates the tender 28-joint count (TJC28), the swollen 28-joint count (SJC28), erythrocyte sedimentation rate (ESR; mm/hour) and patient global/general health assessment VAS (mm)
- The DAS28 will automatically be calculated within the MACRO eCRF during the course of the study, and this may be used to inform decisions regarding treatment; the value calculated will also be computed at the analysis stage from the stored DAS28

components [18, 19]. DAS28 remission (primary endpoint) will be deemed to have been achieved if DAS28 ≤2.6.

- Tender joint count: The number of tender and painful joints will be determined by examination of 28 joints. Joints will be assessed for tenderness by pressure and joint manipulation on physical examination. The patient will be asked for pain sensations on these manipulations and watched for spontaneous pain reactions. Any positive response on pressure, movement, or both will then be translated into a single tender versus non-tender dichotomy. Joint assessments will be performed by an independent assessor to minimize bias. The same assessor should preferably perform the TJC and SJC for a given patient at each visit to minimize inter-observer variation. The independent joint assessor (IJA) will not be involved in patient care and will be instructed not to discuss disease activity or treatment with patients or the Principal Investigator.

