##### **Change from baseline to Week 24 in DAS28ESR score**

An additional analysis will be carried out using the DAS28ESR as a continuous measure instead of converting to a binary response, since information is lost when a variable is dichotomised.

The continuous DAS28ESR score will be summarised by visit, overall and by treatment arm.

The continuous DAS28ESR score will be analysed using a repeated measures mixed-effects linear regression model, with the change from baseline in DAS28ESR score at Weeks 4, 12 and 24 as the dependent variable, adjusting for baseline DAS28ESR, trial arm, age (at baseline), gender, smoking status (binary; current or previous vs never), week and trial arm-by-week interaction as fixed effects and including the participant as a random effect. An unstructured covariance matrix will be used to describe the correlations between DAS28ESR and visits for a participant. If this model fails to converge then other covariance matrix structures will be considered. The denominator degrees of freedom will be calculated using the Kenward-Roger method. All available data will be used in the analysis and no imputation will be made for missing data. If the model assumptions are not met, then transformations of variables or alternative regression models may be used.

The marginal mean estimate, mean difference between trial arms and associated Wald 95% CIs and p-values will be reported for each time point.

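### Entering an ESR of 0 as 0.001 takes 4.84 points off DAS28, so a patient with ESR 0 is scored as in remission whatever the joint counts

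*SAP*

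**What the plan says.** SAP section 7.1 builds DAS28ESR from the tender joint count, the swollen joint count, the patient's general health VAS (GH) and the natural logarithm of ESR. Because the logarithm of zero does not exist, it adds: "Note that ESR values of 0 will be input as 0.001 to allow for them to be compatible with the DAS28 formula". The same paragraph gives the scale: "The DAS28ESR ranges from 0-10 with higher scores indicating greater disease activity". Remission is a score of 2.6 or less. Protocol section 8.1 uses the same cut-off: "DAS28 remission (primary endpoint) will be deemed to have been achieved if DAS28 ≤2.6". The protocol does not mention the ESR substitution.

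The score is also used as a continuous outcome. Under SAP section 11.5.1.2, "The continuous DAS28ESR score will be analysed using a repeated measures mixed-effects linear regression model", with change from baseline at Weeks 4, 12 and 24 as the dependent variable. Baseline DAS28ESR is a covariate in that model and in the primary logistic model (section 11.5.1).

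**The concern.** On a log scale, 0.001 is not a small adjustment to zero. It lies three factors of ten below an ESR of 1, and each factor of ten costs 0.70 × ln(10) = 1.61 DAS28 points. A value chosen only to make the formula computable can therefore outweigh everything else in the score.

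If it does, patients with many tender and swollen joints are counted as remitters. The error would enter:

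- the primary endpoint;
- remission at Week 12 (A vs B) and at Weeks 12 and 24 (B vs C);
- sustained remission;
- the repeated-measures logistic model;
- the reference variable of the ROC analysis in section 12.1.

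An ESR of 0 at baseline would also create an extreme covariate value, and one at any visit would create an extreme value in the continuous models. The planned sensitivity analyses cover the per-protocol set, missing data and missing joint assessments. None varies the ESR rule.

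**Working it through.** **Inputs**

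- Formula (SAP 7.1): DAS28ESR = 0.56√TJC + 0.28√SJC + 0.014 GH + 0.70 ln(ESR).
- Ranges (Protocol 4.2): TJC 0 to 28, SJC 0 to 28, GH 0 to 100 mm.
- Substitute for ESR 0: 0.001 (SAP 7.1).
- Remission: score ≤ 2.6 (SAP 7.1, Protocol 8.1).
- Planned arm sizes (SAP 9): A 44 to 46, B 16 to 30. Target remission 68% in A and 25% in B, a difference of 43 points.

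**The SAP's own range.** With TJC, SJC and GH all 0 and ESR = 1, the score is 0.70 × ln(1) = 0. The stated lower limit of 0 therefore corresponds to an ESR of at least 1. With ESR = 0.001 the minimum is −4.84, so the substitution breaks the stated range.

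**Largest score possible at ESR 0**

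- ESR term: 0.70 × ln(0.001) = −4.835.
- Other terms at their maximum: 0.56√28 + 0.28√28 + 0.014 × 100 = 2.963 + 1.482 + 1.400 = 5.845.
- Sum: 5.845 − 4.835 = 1.01, which is below 2.6.

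Over all whole-number combinations of the three components (29 × 29 × 101 = 84,941), every one is remission at ESR 0.001, and 77,325 give a negative score. At ESR 1 only 12,348 are remission. These counts describe the formula; they are not patient frequencies.

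Any substitute below exp((2.6 − 5.845)/0.70) ≈ 0.0097 makes remission automatic.

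**Individual patients, by the value used for ESR 0**

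| TJC, SJC, GH | 0.001 (SAP) | 0.5 | 1 | 2 |
|---|---|---|---|---|
| 10, 8, 60 | −1.43 | 2.92 | 3.40 | 3.89 |
| 5, 4, 50 | −2.32 | 2.03 | 2.51 | 3.00 |
| 28, 28, 100 | 1.01 | 5.36 | 5.84 | 6.33 |

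First row at ESR 1: 0.56√10 + 0.28√8 + 0.014 × 60 = 1.771 + 0.792 + 0.840 = 3.403. Under the SAP: 3.403 − 4.835 = −1.43.

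**Effect of one misclassified patient**

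- Arm B remission rate: 1/16 = 6.3 points, or 1/30 = 3.3 points.
- Arm A remission rate: 1/44 = 2.3 points, or 1/46 = 2.2 points.
- Arm B mean DAS28, against ESR set to 1: 4.84/16 = 0.30, or 4.84/30 = 0.16.
- Unadjusted A:B odds ratio at the planned rates (30/44 against 4/16): (30/14)/(4/12) = 6.4. With one extra Arm B remitter (5/16): (30/14)/(5/11) = 4.7.

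**The case against.** The arithmetic is not in dispute. The case on the other side is about how often and how much the rule matters.

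- **Other rules override the score.** Under SAP sections 7.1 and 11.2.3, a patient with another component missing has no score and is imputed as a non-responder, and a patient who stopped early for lack of efficacy is a non-responder from then on. This stands: remission is automatic for ESR-0 patients outside those two groups.
- **No affected patient is shown.** The documents do not report the number, timing or arm of ESR-0 values, and the sentence may be precautionary. This stands too. The net effect could be nil, and its direction is unknown because zeros could occur in either arm.
- **Not every ESR-0 patient changes status.** Compared with ESR set to 1, remission changes only when the other three terms sum to more than 2.6. The patient with 5 tender joints, 4 swollen joints and GH 50 is in remission either way. That patient's continuous score is still 4.84 points lower, about half the stated 0 to 10 scale.
- **Diagnostics are planned.** Section 11.5.1 includes Cook's distance, with a sensitivity analysis that removes influential observations, and section 11.5.1.2 allows transformations or other models. These may flag an extreme covariate or residual. They do not correct an outcome coded as remission by construction.
- **The replacement value is a choice.** For CRP below its detection limit the SAP takes a midpoint (2.5 for values under 5, section 11.2); by analogy, ESR 0 might become 0.5. Between 0.5 and 1, status differs only for patients whose other terms sum to more than 2.6 and at most 3.085 (2.6 + 0.485). That supports reporting both values. It does not support 0.001, since either alternative removes automatic remission.

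**Conclusion.** The rule is wrong as written and should be changed before analysis. From the SAP's own formula, cut-off and component ranges, any score calculated at ESR 0 lies between −4.84 and 1.01. It is therefore always remission, and it can fall outside the range stated in the same paragraph. This conclusion needs no assumption about the data.

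The size of the effect on the trial does depend on unreported data. Each ESR-0 patient whose other terms sum to more than 2.6, and who is not already a non-responder under another rule, adds a false remitter: 3.3 to 6.3 points in Arm B or 2.2 to 2.3 points in Arm A, against a target difference of 43 points. With Arm B possibly as small as 16, one record can visibly move the primary odds ratio.

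**What to change.** Replace the sentence in SAP section 7.1 with: ESR values of 0 mm/hr will be set to 1 mm/hr (ESR term = 0) in every DAS28ESR calculation, at every visit including baseline. This restores the stated lower limit of 0.

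Also:

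- recompute all scores from the stored components, and check whether the MACRO-derived scores used a different rule;
- list the ESR-0 records by arm and visit, with the score and remission status under each substitute;
- add a sensitivity analysis of the primary endpoint with ESR 0 set to 0.5 (ESR term −0.49), because borderline patients can change status between 0.5 and 1.

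Record the change in the SAP amendment log before the statistician receives the arm codes (Protocol 12.10). If the codes have already been released, report the results under both the old and the new rule. The cost is one sentence, one log entry, one line of code and one additional model run. No new data are needed.
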